Specific Aim 1 (Primary Aim): To determine the effectiveness of ZNS treatment in reducing drinking on the primary outcome measure: drinks per week (measured using the Timeline Followback Method), for eight weeks at a target dose of 600 mg of ZNS daily for 160 heavy-drinking, alcohol-dependent veterans. We hypothesize that ZNS treatment will reduce the heavy drinking days per week and the total drinks per week significantly more than the placebo and that the benefits will persist at three months follow-up after treatment.

Specific Aim # 2 (Secondary Aim): To examine the effects of ZNS treatment on heavy drinking days per week, , percentage of subjects with no heavy drinking days (PSNHDD) the urge to drink (craving), biomarkers of alcohol intake, clinical global impression, medication tolerability, and other patient-centered outcomes. We hypothesize that ZNS will demonstrate significantly greater improvements than the placebo on these measures by the treatment endpoint as well as at follow-up.

Specific Aim #3 (Secondary): To use telephone-based daily process data collection to elucidate the mechanism of action of ZNS as it relates to changes in craving, anxiety, and genetic variation. *This method has been shown to elucidate the mechanism of action of topiramate, as well as its pharmacogenetic interactions.* We hypothesize that ZNS' effects will be moderated by genetic variation, craving, and anxiety, but mediated through changes in self-efficacy to reduce heavy drinking.

Specific Aim #4 (Exploratory): The exploratory aim is to examine the pharmacogenetic interactions between ZNS and the therapeutic response. We hypothesize that both the long (L) allele of the VNTR polymorphism in exon 3 of the *DRD4* gene and the CC genotype of the *DBH* rs1611115 (C-1021T) SNP will show a pharmacogenetic effect with ZNS, as evidenced by a greater reduction in drinking than for the short (S) allele and T carriers respectively.

Specific Aim #5 (Exploratory) To compare ZNS and placebo-treated subjects on pre- and post-treatment changes in measures of stress-reactivity (i.e., stress-induced anxiety, alcohol craving, autonomic nervous system activity), cue-elicited craving, and impulsivity. We hypothesize that ZNS will attenuate stress-reactivity, cue-elicited craving, and impulsivity more than placebo in a stress laboratory paradigm, and that attenuation of those measures will be associated with reduction in drinking.

4. BACKGROUND:

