6.D.4. Visits 2-17 (Treatment and End-of-Treatment Visits): Subjects will return weekly for study visits to meet with the research nurse, complete questionnaires, and receive medical management (MM, described below). At study midpoint (i.e., 8 weeks after starting medication), another CBC, and chemistry/electrolyte panel (including a serum GGT), will be obtained. Urine drug screens will be checked weekly, and pregnancy tests (in all females of reproductive potential) are repeated monthly. At the end of week 16 (endpoint), subjects will complete the packet of questionnaires and will be interviewed by the research evaluator concerning their alcohol-related symptomatology using the Alcohol Use Disorders section of the SCID over the past 30 days. Subjects will also be interviewed by the research nurse about their use of concomitant medications, occurrence of adverse events, compliance with the protocol, and their assessment of the effectiveness and acceptability of the treatment procedures. A blood sample for measurement of serum GGT and metabolic labs will be obtained to provide an index of potential hepatic effects and to assess the validity of self-reported drinking. A urine drug screen and urine pregnancy screen (in all females of reproductive potential) will be obtained at this time as well. The nurse and study physician will monitor continuing adverse events to their resolution. Subjects requesting (or clearly needing) additional treatment for alcohol problems are (if clinically indicated) discontinued from the study protocol and referred to local treatment centers. Similarly, at the end of the treatment trial, subjects whose drinking requires continued treatment will be referred for such treatment. All subjects will be asked to complete an end-of-treatment evaluation to facilitate planned intention-to-treat analyses. All subjects will be informed of these procedures prior to study enrollment.

6.D.5. Visit 10b (Stress Lab Session 2): This visit will occur between weeks 8-16 of being on the study medication. The session will use the same audio tapes created for the baseline stress lab and the session will be identical to the baseline stress lab (assessments), with the exception of the randomized order of the presentation of the audio tapes.

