6.H.2. Imagery Script Development: First, scripts for the guided imagery induction will be developed. The **stress imagery script** will be based on subjects' description of a recent personal stressful event that is self-rated as an 8 or above on a 10-point Likert scale, where 1 = "not at all stressful" and 10 = "the most stress I have recently felt in my life". Examples of acceptable stressful situations include breakup with significant other, a verbal argument with a significant other or family member or unemployment-related stress, such as being fired or laid off from work. A **neutral-relaxing script** will be developed from the subjects' commonly experienced neutral-relaxing situations. Neutral-relaxing events that involve nicotine or alcohol/drugs will not be allowed. An **alcohol craving cue imagery script** will be based on subjects' description of a recent event in which alcohol was consumed. Stressful situations will not be acceptable for these latter two types of scripts.

A 'script' or description of each situation will be developed using Scene Development Questionnaires which obtain specific stimulus and response details, including specific physical and interpersonal context details, verbal/cognitive attributions regarding the people involved, and physiological and bodily sensations experienced for the situation being described. The three scripts for each subject will then be recorded on an audiotape (or similar technology) for guided imagery in the laboratory sessions. The order of stress, alcohol-cue, and neutral scripts will be assigned randomly, and counterbalanced across subjects, prior to the first stress lab. Detailed procedures are outlined in the imagery development procedures manual (88).

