6.H.3. Manipulation Check for Script Development: All three scripts will be rated on a Likert scale from 1 to 10 on a standard rating form (Independent Rating Scale) by two objective independent raters for stressful and emotional content. If a script scores below a rating of 8 for stressful content on a five-point rating scale the subject will be asked to develop a new script prior to the laboratory sessions. These procedures ensure that the stress scripts of all subjects are equated in intensity and content. It further ensures that differences in stress reactivity are not due to differences in intensity and emotional content of the stressor. The procedures for development of imagery scripts, rating of scripts for content and physiological activation are similar to those used by Miller et al. (89) and have been successfully used in previous work by co-investigators.

6.H.4. Imagery & Relaxation Training: subjects will be introduced to all self-report measures and instructed how to complete them. In order to minimize baseline imagery variability participant will be given relaxation and imagery training, as described in the imagery training procedures manual (88). Relaxation training will be approximately 20 minutes and will consist of progressive muscle relaxation technique. The imagery training will consist of two types of visualizations. First, participants will be asked to visualize an unemotional scene, such as reading a magazine. Second, they will be presented with an unemotional but physically arousing scene, such as exercising in a gym. Here, the emphasis will be placed on assuring that participants are aware of physiological changes, increased heart rate, or breathing. Subjects will be given instructions throughout the imagery exercises regarding the process of imagining the scenes and maintaining the visualization for an extended period of time.

The order and content of the imagery conditions will not be revealed to the subject or to the research staff conducting the sessions. **The neutral script will always occur in between the stress script and alcohol-cue script, the both of which will be randomized to occur before or after the neutral script.** In the imagery task, the subjects will be asked to imagine the situation being described vividly, 'as if' he/she is in the specific situation, until asked to stop. The imagery script will be played to the subject over headphones and the subject will be required to imagine the situation for 5 minutes.

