6.I.4. To use telephone-based daily process data collection to elucidate the mechanism of action of ZNS as it relates to changes in craving, anxiety, self-efficacy, and genetic variation (Specific Aims 3, 4): Multilevel models will be used to evaluate the associations between craving, self-efficacy, anxiety, and daily drinking and how these associations vary as a function of medication group and GRPS. Similar to Kranzler et al. (82), we will focus on predicting nighttime drinking (i.e., drinks consumed after the early evening report), but here we will use psychological measures reported during the early evening in the daily survey. Nighttime drinking levels will be determined by subtracting the number of drinks consumed during the current day from the total number of drinks consumed for that day (reported the following day). We will follow the general analysis scheme used by Kranzler et al. (82), but will use mixed effects/multilevel models, rather than generalized estimating equations (GEE) models (99) because mixed models give unbiased estimates under less restrictive assumptions about missing data. We will examine the number of drinks consumed (using a Poisson model or negative binomial model if there is overdispersion). We will use the HGLM module of the HLM7 program, as it is more flexible for some of our models than PROC GLIMMIX in SAS. Analysis will focus on the last eight weeks of treatment, consistent with the analyses of outcomes in Aim 1. We will test the hypothesis that ZNS reduces nighttime drinking and that craving, anxiety, and GRPS act as moderators of this effect. We anticipate greater ZNS effect in subjects with greater anxiety, craving and genetic loading (greater GPRS). We will examine whether ZNS's effect on drinking is mediated by self-efficacy using the approach of Kraemer et al. (100, 101), such that self-efficacy is significantly affected by ZNS treatment, and has a main or interaction effect on nighttime drinking in the model containing both treatment and the potential mediator as predictors.

6.I.5. Stress Reactivity Lab (Specific Aim 5): We will compare pre- and post-treatment changes in levels of anxiety, craving, and impulsivity measures induced by stressful and alcohol-cue imagery in the lab. We will test if the mean induced changes are attenuated by ZNS more than placebo using ANCOVA. The amount of reactivity pre-treatment will be explored as a covariate in secondary outcome models.

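### The Aim 5 analysis leaves induced change undefined and makes no use of the neutral script, so the planned ANCOVA alone cannot show that any attenuation is specific to stress or alcohol cues

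*Combined protocol and SAP*

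**What the plan says.** Section 3 lists Aim 5 as exploratory and states: "We hypothesize that ZNS will attenuate stress-reactivity, cue-elicited craving, and impulsivity more than placebo in a stress laboratory paradigm". It adds that attenuation of these measures should go with reduced drinking.

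The lab design includes a control condition. Under 6.H.2, "A neutral-relaxing script will be developed from the subjects' commonly experienced neutral-relaxing situations". Under 6.H.4, "The neutral script will always occur in between the stress script and alcohol-cue script". Table 3 takes craving and emotion ratings and a BP/HR recording at T 0, before imagery, and repeats them after imagery and after recovery. It gives Scripts #2 and #3 the same schedule as Script #1. Section 6.D.3 says the measures are identical for the three tapes and that the session is repeated on medication. Section 6.D.5 makes the second session identical, "with the exception of the randomized order of the presentation of the audio tapes".

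The analysis in 6.I.5 is brief. It compares pre- to post-treatment changes in "levels of anxiety, craving, and impulsivity measures induced by stressful and alcohol-cue imagery in the lab". The test is: "We will test if the mean induced changes are attenuated by ZNS more than placebo using ANCOVA". The only covariate mentioned is pre-treatment reactivity: "The amount of reactivity pre-treatment will be explored as a covariate in secondary outcome models".

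**The concern.** A neutral script is in the design so that the response to the imagery procedure can be separated from the response to its content. Section 6.I.5 names the other two scripts and not this one, and the neutral response appears in no Aim 5 hypothesis, outcome definition, contrast or covariate. Nor does the section say whether an induced change is measured from the script's own T 0 rating, from the neutral script, or not from a reference at all.

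The Aim 5 claim is specific to stress and to alcohol cues. If zonisamide blunts the response to being led through imagery of any kind, the stress-script and cue-script comparisons will both favour zonisamide with nothing specific to stress or alcohol behind it. Randomisation and the pre-treatment covariate do not help, since such an effect arises on active drug after randomisation. The mechanism that Aim 5 sets out to describe would then be misread.

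**Working it through.** **No plan figure to reproduce.** Section 6.I.6 covers Aims 1-3 and 6.I.7 covers Aim 4. Neither gives a sample size, SD, effect size or alpha for Aim 5. The lab is optional (6.D.3), so the number per arm is unknown and at most 80 (6.D.2). I take 40 and 80 per arm and two-sided 0.05 as assumptions.

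**Simulation inputs (all assumed, in rating units).** SDs: stable subject level 0.7; session level 0.3; stable response to any imagery 0.4; stable extra response to stress 0.5; measurement error 0.4 on each rating. There were 2000 trials per cell. Each on-treatment outcome was analysed by ANCOVA on the matching pre-treatment outcome, for three definitions of the outcome. The entries are percentages of trials declaring an arm difference.

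| True drug effect | n per arm | Raw post-imagery stress rating | Stress change from T 0 | Stress change minus neutral change |
|---|---|---|---|---|
| None | 80 | 5.6 | 6.2 | 5.2 |
| All ratings lowered by 0.3, including T 0 | 80 | 80 | 5.1 | 5.7 |
| Response to every script lowered by 0.2 | 80 | 46 | 43 | 4.6 |
| Response to every script lowered by 0.3 | 80 | 80 | 76 | 4.9 |
| Response to every script lowered by 0.2 | 40 | 26 | 24 | 4.6 |
| Response to every script lowered by 0.3 | 40 | 52 | 48 | 4.8 |
| Stress response alone lowered by 0.3 | 80 | 82 | 76 | 54 |
| Stress response alone lowered by 0.3 | 40 | 51 | 46 | 30 |

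**Closed-form check at 80 per arm.**

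- Stress change from T 0: variance = 0.4² + 0.5² + 2(0.4²) = 0.73. Of this, 0.16 + 0.25 = 0.41 is shared between sessions, so the between-session correlation is 0.41/0.73 = 0.562. Residual SD after ANCOVA = √[0.73(1 − 0.562²)] = 0.707. SE = 0.707√(2/80) = 0.112. For an effect of 0.3, z = 2.68, and with critical value 1.976 the rejection rate is about 76%.
- Stress minus neutral: variance = 0.5² + 4(0.4²) = 0.89, between-session correlation 0.25/0.89 = 0.281, residual SD √[0.89(1 − 0.281²)] = 0.905, SE 0.143. An effect common to all scripts cancels, so rejection stays at the nominal level. A stress-specific effect of 0.3 gives z = 2.10 and power of about 55%.

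Both agree with the simulation.

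**Cost in precision more generally.** If the stress and neutral changes have equal variance and within-session correlation r, the SE of the contrast relative to that of one script is √(2(1 − r)): 1.41 at r = 0, 1.00 at r = 0.5 and 0.77 at r = 0.7. Precision is lost when r is below 0.5. In the simulated case the ratio after covariate adjustment is 0.905/0.707 = 1.28.

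**The case against.** **Silence is not a decision.** An induced change could have been meant as change from T 0, or even as difference from neutral. This stands: a reader might infer that the investigators chose to discard the neutral data, and the documents do not show that. They show a contrast left undefined.

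**T 0 ratings already protect the comparison.** A reader might infer that any sedation, relaxation or rating habit on zonisamide would pass as attenuated reactivity. That goes too far. A shift already present before imagery cancels in change from T 0 (5.1% in the table), provided that change is the outcome, which 6.I.5 does not state. A drug effect on the response to imagery itself does not cancel.

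**The rates are hypothetical.** They are. Section 8.B reports more somnolence than placebo in epilepsy trials (17% vs 7%) and more fatigue in an obesity trial, so a non-specific effect is conceivable. Nothing in the documents shows one on imagery ratings. The rate near 5% for the contrast follows from assuming equal shifts across scripts. Equal shifts may fail if ratings after a relaxing script lie close to the scale floor of 0.

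**Script order.** Since order is randomised afresh for the second session, a reader might infer that leaving it out biases the comparison. It does not: order is randomised and counterbalanced across subjects (6.H.2), so omitting it costs precision at most.

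**The neutral contrast has faults of its own.** This stands. Neutral is always second, so the contrast is aliased with position, and no order term can separate the two. Neutral also follows an emotive script, and carry-over may differ by arm.

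**Conclusion.** The point holds in a limited form. As written, 6.I.5 can show that zonisamide and placebo differ in the response during the stress or alcohol-cue script. It cannot show that the difference is specific to stress or alcohol cues, because change from T 0 does not remove a drug effect on the response to any imagery and the neutral data that could reveal one are not used.

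Under the assumptions above, a purely non-specific response effect of 0.2 to 0.3 units would be read as stress attenuation in 43% to 76% of trials at 80 per arm and 24% to 48% at 40 per arm. These rates illustrate the mechanism and do not forecast this trial.

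The contrast covers craving, anxiety and other emotion ratings, and BP/HR. It covers impulsivity only if the BART is repeated with each script, as 6.D.3 implies. Table 3 lists BART and BIS only at T −20, and the two places need to be reconciled.

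Aim 5 is exploratory, so the primary drinking conclusion is untouched. This is a cheap improvement to a mechanistic analysis.

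**What to change.** Amend 6.I.5 as follows.

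1. Define reactivity, for each script and measure, as the post-imagery value minus that script's own T 0 value.
2. Model session-2 reactivity for all three scripts, with repeated measures within subject. Include medication, script, medication × script and the matching session-1 reactivity. Script order may be added for precision only.
3. Report medication × (stress vs neutral) and medication × (cue vs neutral) beside the single-script ANCOVA, with estimates and intervals for each script by arm. Claim stress- or cue-specific attenuation only if these contrasts support it.
4. State the limits: possible loss of power, aliasing with the middle position, and carry-over from the first script.
5. Reconcile 6.D.3 and Table 3 on when the BART is given, and restrict the script contrasts to measures taken with each script.

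The cost is wording in the analysis plan, with no new data. The statistical cost is power when responses to different scripts are weakly correlated. In the simulated case, power for a true stress-specific effect of 0.3 falls from 76% to 54% at 80 per arm and from 46% to 30% at 40 per arm. That is the reason to keep the single-script ANCOVA in the report.

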Zonisamide (ZNS), an anticonvulsant acting on serotonergic, dopaminergic, GABAergic, and glutamatergic neurotransmitter systems, has shown great promise in treating individuals with AD. We conducted a pilot study (N = 40) showing that ZNS, given once daily, significantly reduced heavy drinking and overall drinking compared to a placebo in subjects with AD and was very well tolerated ([name] et al., 2010). Several anticonvulsant medications have shown promise in treating alcohol dependence, most notably topiramate, but ZNS has advantages over topiramate, including a more favorable side effect profile and a simpler once-a-day dosage regimen. ZNS also has direct pharmacologic action on dopamine and serotonin, which may make ZNS particularly effective in treating co-occurring psychiatric disorders. Topiramate's effectiveness is limited by its poor tolerability, so better tolerated medications are needed.

DESIGN: We propose a 16-week randomized, double blind, placebo-controlled trial designed to determine the effectiveness of ZNS treatment for reducing heavy drinking and overall drinking in 160 treatment-seeking, regularly heavy drinking, alcohol-dependent veterans who want to quit drinking or reduce consumption to non-hazardous levels. We will use state-of-the-art methodology and outcome assessments, including medical management (MM) therapy (a minimal behavioral intervention aimed at reinforcing treatment goals and adherence to medication), which is simple and easily implemented in primary care settings. The use of MM in the study will increase the generalizability of results, allowing a more accurate assessment of ZNS's effectiveness than if a more intensive behavioral intervention were to be used. To demonstrate ZNS's effectiveness in a representative veteran sample, we will include veterans with co-morbid mood and anxiety disorders.

We also plan to explore the interaction between genotype and medication on drinking outcomes, targeting two functional polymorphisms: The first SNP is in the gene *DBH*, and we have found that it moderates the treatment response to naltrexone in veterans. The other is a functional variable number, tandem repeat (VNTR) polymorphism located in exon 3 of the *DRD4* gene that has been shown previously to moderate the effects of medications on drinking behavior. Both polymorphisms are directly relevant to ZNS's mechanism of action and alcoholism pathophysiology.

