We will use the percentage of subjects with no heavy drinking days (**PSNHDD**) as the primary outcome variable. This outcome is the FDA recommended endpoint for pivotal trials, and is described in Falk et al., (2010). The PSNHDD can be derived from each subject's TLFB data. An important initial consideration in considering effectiveness will be to identify baseline differences between groups that may have occurred despite randomization. **Successful outcomes during the treatment trial will be defined in terms of a statistically significant difference on the primary outcome measure: PSNHDD, compared during the 8 weeks of active treatment at the target dose, allowing for a 6 week grace period for the medication titration.** For all analyses, heavy drinking days will be defined as follows; for men > 5 drinks in a day and for women > 4 drinks in a day. Patients will be followed irrespective of whether they continue to receive medication treatment, so that analysis will include all data available for the 8-week treatment period. The analysis will be **intent-to-treat**, and dropouts will be considered as having relapsed to heavy drinking. We will use a logistic regression analysis with PSNHDD as a categorical dependent variable. Medication condition (placebo or ZNS) will be the main independent variable, and we will include the variables of early onset of alcoholism (EOA, binary), and the use of additional psychotropics (e.g., antidepressants, a binary variable) as covariates. The α will be set at .05 for the primary outcome variable. Between site differences will be explored.

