6.I.6. Sample Size And Power Estimate (Specific Aims 1-3):

For the primary outcome PSNHDD: Based on the trend in the pilot study favoring ZNS with 12 subjects in the ZNS group without relapse to heavy drinking, and only 7 in the placebo group, we estimated the power with the previously planned sample size. Based on these proportions, we should be well powered (>89%) to detect a difference in PSNHDD with 80 in each group. Since dropouts will be counted as relapsed to heavy drinking, we will still be powered at that level, regardless of the number of dropouts. Even in the event that we don't recruit as many subjects as expected (e.g., N=64 in each group, approximately) we estimate the estimated power will be about 76% to detect a difference between the medication and placebo.

For secondary outcomes: Based on the effect sizes from our pilot study of ZNS (showing a small effect size on heavy drinking and a moderate effect size on total drinking), we estimated that a study with **N=160** (subjects) would be well powered (>.98) to detect a significant difference on the secondary outcomes heavy drinking days per week, and total drinks per week. In our pilot study we ran a linear mixed models and found a decrease in drinking of 1.4 drinks per week for the controls versus 2.2 drinks per week for ZNS. The variance in the decrease in drinking (slope) was approximately 0.9. Assuming similar results, a Monte Carlo simulation in Mplus showed that with a sample of 160 subjects evenly split between groups and measured weekly over 12 weeks there is power of 0.98 to detect a significant difference in slopes between groups. Also, in our pilot study we found a decrease in heavy drinking days per week of 0.2 for the controls versus 0.3 for ZNS. The variance in the decrease in drinking (slope) was about 0.1. Assuming similar results, a Monte Carlo simulation in Mplus showed that with a sample of 160 subjects evenly split between groups and measured weekly over 12 weeks there is power of 0.99 to detect a significant difference in slopes between groups. **Even if dropouts reached 40%, we will be well powered (>.80) for detecting differences on secondary outcomes.**

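### Power for the no-heavy-drinking-days outcome is not fixed above 89% whatever the dropout: scoring dropouts as relapsed protects the sample size, not the success rates

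*Combined protocol and SAP*

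**What the plan says.** Section 6.I.2 makes PSNHDD the primary outcome variable, sets alpha at 0.05 and states that "dropouts will be considered as having relapsed to heavy drinking". The analysis is a logistic regression: "We will use a logistic regression analysis with PSNHDD as a categorical dependent variable".

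Section 6.I.6 takes its effect size from the pilot study, "with 12 subjects in the ZNS group without relapse to heavy drinking, and only 7 in the placebo group". Section 3 gives the pilot's total as 40; the arm sizes are not stated. From these counts the section concludes that "we should be well powered (>89%) to detect a difference in PSNHDD with 80 in each group". For a shortfall to roughly 64 per group, "we estimate the estimated power will be about 76% to detect a difference between the medication and placebo".

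On dropout, the same section says of PSNHDD: "Since dropouts will be counted as relapsed to heavy drinking, we will still be powered at that level, regardless of the number of dropouts". For the secondary outcomes it does test a dropout rate: "Even if dropouts reached 40%, we will be well powered (>.80) for detecting differences on secondary outcomes". No dropout rate is assumed or tested for PSNHDD.

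**The concern.** The power of a comparison of two proportions depends on the number analysed and on the two success rates. The scoring rule secures the first. It does so by turning every dropout into a failure, including any who would have finished with no heavy drinking days, so it can move the second.

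The sentence in section 6.I.6 therefore replaces a sensitivity check with an assurance, on the outcome where dropout counts most directly. A reader would conclude that retention cannot affect the chance of a positive primary result. The protocol's own background suggests otherwise. Section 4.B.1 reports that a conservative treatment of dropouts in a topiramate trial cut the effect on heavy drinking days from 16.19% to 8.44%, and section 7 names retention as a possible pitfall of the long titration.

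**Working it through.** **Inputs.** Pilot successes 12 and 7 (section 6.I.6); pilot N = 40 (section 3); 80 per arm (section 6.D.2); alpha 0.05 (section 6.I.2). Assumed: two-sided testing and pilot arms of 20 and 20, so the rates are 12/20 = 60% and 7/20 = 35%.

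**Formula.** Two-proportion normal approximation, no continuity correction, with p̄ = (p1 + p2)/2:

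power = Φ{ [ |p1 − p2| − 1.96 √(2p̄(1 − p̄)/n) ] / √( [p1(1 − p1) + p2(1 − p2)]/n ) }

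**Step 1: reproduce the stated figure.** With 60% vs 35% and n = 80: (0.25 − 0.1548)/0.0764 = 1.246, and Φ = 0.894. This matches the plan's figure of more than 89%. It also supports the 20/20 split: 19 ZNS and 21 placebo gives 97%, and 21 and 19 gives 73%.

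**Step 2: apply the scoring rule.** Let d be the dropout proportion. If dropout is equal by arm, unrelated to what the outcome would have been, and not already in the pilot rates, both rates are multiplied by (1 − d) and n stays at 80. At d = 0.20 the rates are 48% and 28%: (0.20 − 0.1504)/0.0751 = 0.660, and Φ = 0.745.

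| Dropout, each arm | ZNS vs placebo success | Power |
|---|---|---|
| 0% | 60.0% vs 35.0% | 89% |
| 10% | 54.0% vs 31.5% | 83% |
| 20% | 48.0% vs 28.0% | 75% |
| 30% | 42.0% vs 24.5% | 65% |
| 40% | 36.0% vs 21.0% | 56% |

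At 20% dropout this is lower than simply losing those patients with the rates unchanged (64 per arm, 82%).

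**Step 3: vary the assumptions.**

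- *Dropouts half as likely as average to have succeeded* (rates multiplied by 1 − 0.5d): 83% at 20% dropout, 75% at 40%.
- *Pilot rates already count dropouts as failures* (rates multiplied by (1 − d)/(1 − pilot dropout), again with dropout equal by arm and unrelated to outcome). With pilot dropout of 20%: 89% if trial dropout is 20%, 70% if it is 40%. With pilot dropout of 10%: 82% and 62%. If the trial retains better than the pilot, power rises: pilot 15% and trial 10% gives 92.5%.
- *Unequal dropout, otherwise as step 2.* 30% on ZNS and 20% on placebo: 42% vs 28%, power 46%. The reverse, 20% and 30%: 48% vs 24.5%, power 88%.
- *Every dropout would have relapsed anyway.* No loss: power stays at 89%. This case can hold only up to 40% dropout on ZNS, because beyond that fewer than 60% of ZNS subjects remain to succeed. At 50% dropout in each arm, ZNS success is at most 50%; against 35% that gives 48%.

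**Step 4: the two stated powers.** At 60% vs 35% with no dropout:

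| Method | 80 per arm | 64 per arm |
|---|---|---|
| Uncorrected (formula above) | 89% | 82% |
| Continuity-corrected (subtract 1/n from the difference) | 86% | 76% |
| Fisher exact | 86% | 76% |
| Wald test of the log odds ratio | 88% | 80% |

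The plan's figure at 80 fits the uncorrected row. Its figure at 64 fits the corrected or Fisher row. None of these methods gives both.

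**The case against.** The 75% at 20% dropout depends on a particular scenario. A 20/20 split puts all 40 pilot subjects in the denominators, so any pilot dropout was probably already scored one way or the other. If they were scored as failures and trial dropout resembles the pilot's, the 89% stands. Section 4.B.2 says few subjects dropped out of earlier ZNS studies. Section 6.I.2 plans follow-up whether or not medication continues, and section 6.D.4 asks everyone for an end-of-treatment evaluation, so stopping the drug need not make someone a dropout. If most true dropouts would have relapsed, little is lost. More dropout on placebo than on ZNS can even raise power.

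All of this limits the likely size of the loss, and no document supports one dropout rate for this outcome. It does not rescue the sentence, which claims that power is the same for any number of dropouts. Each of these arguments needs a condition on how many drop out, from which arm, or how they would have fared.

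Two further points are fair. Section 3, Aim 1, names drinks per week as the primary measure and lists PSNHDD under Aim 2. This point follows sections 6.I.2 and 6.I.6; if section 3 governed, it would concern a secondary outcome. On the formulas, the plan says only approximately 64 and about 76% and names no method, so the mismatch is with the standard methods tried above.

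**Conclusion.** The concern holds. The statement that PSNHDD power is unaffected by the number of dropouts is wrong as written. Under the step 2 conditions, power falls from 89% to 75% at 20% dropout and to 56% at 40%. Under others the loss is smaller or absent, and with unequal dropout power can move in either direction. The sizes rest on the assumed 20/20 pilot split, two-sided testing, a two-proportion approximation to the planned logistic regression, and dropout rates chosen for illustration. The error in reasoning rests on none of these. Separately, the powers quoted for 80 and 64 per arm are not on a common basis. The sample size is not shown to be inadequate; the assurance about it is unsupported.

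**What to change.** In section 6.I.6:

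1. Delete the sentence claiming that power holds whatever the dropout.
2. State whether the pilot's 12 and 7 count dropouts as failures, and give the pilot's arm sizes.
3. Give PSNHDD power over 0% to 40% dropout, for equal and unequal dropout by arm, with the assumption about how dropouts would have fared.
4. Name one formula and use it for both sample sizes: 89% and 82% uncorrected, or 86% and 76% corrected. Say that it approximates the planned logistic regression.

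Section 6.E.1 (withdrawal from the study) and section 6.I.2 (follow-up irrespective of medication) should also be reconciled, because together they determine who is scored as a dropout.

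The cost is wording and looking up how the pilot handled dropouts. Sample size, test, alpha and endpoint do not change. The stated power becomes less favourable.
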